7.2 Datasets for Analysis

The following analysis samples are defined for this trial:

- Phase A Safety Sample: Comprises all subjects who took at least 1 dose of brexpiprazole in Phase A.
- Phase B Safety Sample: Comprises all subjects who took at least 1 dose of brexpiprazole in Phase B.
- Phase B Efficacy Sample: All subjects who enter Phase B (ie, receive at least 1 dose of brexpiprazole) and have at least one postbaseline efficacy evaluation in Phase B.
- Phase C Safety Sample: All subjects who are randomized to double-blind treatment and receive at least 1 dose of double-blind IMP in Phase C.
- Phase C Efficacy Sample: Based on the Intent-to-Treat (ITT) principle, the full analysis set of this trial will be composed of all subjects randomized to the double-blind treatment who take at least one dose of IMP in Phase C and who have at least 1 post-randomization efficacy evaluation in Phase C.

For the primary analysis of time to event, all subjects belonging to the Phase C Efficacy Sample will be included in the analysis. Subjects who withdraw early from the trial or who are still in the trial at the end of Week 46 will be considered as providing censored observations.

The observed case (OC) dataset will consist of the actual observations recorded at each visit and will be used to present summaries per trial week.

Protocol 331-201-00079

The LOCF data set will include data recorded at a given Phase C visit or, if no observation is recorded at that visit, data carried forward from the previous Phase C visit. Week 20 data (the last visit of Phase B) will not be carried forward to impute missing values for the LOCF data set.

The LOCF and OC data sets for Phases A and B will be derived in a manner similar to the process described for Phase C.

7.3 Handling of Missing Data

For missing data resulting from early withdrawal from the trial in Phase C, subjects who withdraw early will be censored in the primary efficacy analysis at the time when they withdraw from the trial. In order to assess sensitivity of results due to missing data, two types of analyses will be performed for analyses by visit in Phases B and C: LOCF and OC. The LOCF and OC data sets are defined in the SAP. The OC data set will be used for analyses at each trial visit and the LOCF data set will be used for analyses at the last visit.

7.4 Primary and Secondary Endpoint Analyses

7.4.1 Primary Endpoint Analysis

The primary efficacy endpoint of this trial is time-to-relapse by any criteria as defined in the blinded addendum to this protocol, measured from Week 20 (randomization) into the Double-blind, Randomized Withdrawal Treatment Phase). The objective of the primary analysis is to compare the efficacy of brexpiprazole (2 to 3 mg/day) + ADT with that of placebo + ADT with regard to time-to-relapse. The statistical comparison will be performed by the log-rank test comparing the 2 treatment groups (brexpiprazole + ADT versus placebo + ADT) at an overall nominal significance level of 0.05 (2-sided) using the Double-blind Randomized Withdrawal Efficacy Sample. Interim analyses are planned to be performed at approximately 50% and 75% of events accrual time points using the O'Brian-Fleming boundaries for rejection of the null hypothesis. Details of the interim analyses are provided in [Section 7.4.4](#).

Additionally, for the primary endpoint, a 95% confidence interval for the hazard ratio (brexpiprazole + ADT vs placebo + ADT) will be provided using the Cox Proportional Hazard model with term of treatment in the model.

The Phase C Efficacy Sample will be used in the above analysis. Subjects who withdraw early from the trial or who are still in the trial at the end of Week 46 will be considered as providing censored observations. Subjects who stay in the trial but have no relapses in an interim analysis will be censored at the date of data cut-off for the interim analysis.

Protocol 331-201-00079

7.4.2 Secondary Endpoint Analysis

7.4.2.1 Key Secondary Efficacy Endpoint

The key secondary efficacy endpoints are:

- Change from randomization in the SDS mean total score at Week 46 (LOCF)
- Time to-functional relapse based on SDS criteria.

In order to preserve the overall type I error rate at the 0.05 level, the following testing procedure will be used. If the primary hypothesis of comparing time-to-relapse between brexpiprazole + ADT and placebo + ADT is rejected at an overall nominal alpha level of 0.05, then the hypothesis of comparing first key secondary efficacy endpoint of change from randomization in the SDS mean total score at Week 46 between brexpiprazole + ADT and placebo + ADT will be tested at the 0.05 level. If the hypothesis based on the first key secondary endpoint is rejected at the 0.05 level, then the hypothesis of comparing the other key secondary efficacy endpoint of time-to-functional relapse based on SDS criteria between brexpiprazole + ADT and placebo + ADT will be tested at the 0.05 level.

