3.8 Stopping Rules, Withdrawal Criteria, and Procedures

3.8.1 Entire Trial

If the sponsor terminates or suspends the trial for any reason, prompt notification will be given to investigators, IRBs/IECs, and regulatory authorities in accordance with regulatory requirements.

Two interim analyses are planned so that the trial can be terminated once the primary objective of the trial is met in order to minimize exposure of subjects to placebo in Phase C. The first interim analysis will be performed after 50% of events have been

Protocol 331-201-00079

achieved. If the result of this interim analysis is positive, the trial will be terminated and investigators will be notified. If the interim analysis is negative, a second interim analysis will be performed after 75% of events have been achieved.

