7.1 Sample Size

The primary objective of this trial is to show superiority of brexpiprazole (2 to 3 mg/day) + ADT over placebo + ADT in time to relapse of MDD signs and/or symptoms.

Time-to-relapse criteria are defined in the blinded addendum to this protocol. The 2-sided log-rank test will be used to test for statistical significance of the differences between the 2 survival curves.

Based on the results from a completed randomized withdrawal trial of olanzapine/fluoxetine combination versus fluoxetine monotherapy to assess prevention of relapse in subjects with treatment-resistant depression, it is reasonable to expect that 30% of subjects who receive placebo and 16% of subjects treated with brexpiprazole will relapse in 6 months, a hazard ratio of 0.49 (brexpiprazole + ADT versus placebo + ADT) is derived. Thus, 104 relapse events are needed in this trial to reach 95% power to test the primary hypothesis of the protocol at a 2-sided 0.05 alpha level. The sample size estimates used a 1:1 randomization ratio (brexpiprazole + ADT: placebo + ADT) which allowed 2 interim looks at 50% and 75% of events accrual time points. The O'Brian-Fleming boundaries were used for sample size calculation of the interim analysis so that the first interim analysis will be conducted when 52 relapse events are available and the second interim analysis will be conducted when 78 relapse events are available. The 2-sided alpha levels for these 2 interim analyses are 0.003 and 0.018 respectively, and the alpha left for the final analysis when 104 relapse events are available will be 0.044.

Protocol 331-201-00079

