5.5.4.2 Analysis of Functional Relapse

The secondary efficacy endpoint is time-to-functional relapse based on a 30% increase in Sheehan Disability Scale (SDS) mean total score from Phase C baseline and at least one SDS sub-score at 4 or greater and a SDS total score great than or equal to 7 when all 3 sub-scores are available (or SDS total score greater than or equal to 5 when work/school item does not apply) at Phase C visits. In the event that the SDS phase C baseline is 0, the evaluation will be based on the total SDS and SDS sub-score criteria at Phase C. Time to functional relapse will be the first SDS assessment in Phase C that met the functional relapse criteria.

The Sheehan Disability Scale (SDS) is a self-rated instrument used to measure the effect of the patient's symptoms on work/school, social life, and family/home responsibilities. For each of the three items, scores range from 0 through 10. The number most representative of how much each area was disrupted by symptoms is marked along the line from 0 = not at all, to 10 = extremely. For the work/school item, no response will be entered if the patient did not work or go to school for reasons unrelated to the disorder and a response therefore not being applicable. The Mean total SDS Score will be calculated over the three item scores. All three item scores need to be available with the exception of the work/school item score when this item is not applicable. In the event that work/school item does not apply, the other two items will be averaged as the mean total score.

Event/censor time will be defined as the following: if subjects meet the relapse criteria for functional relapse, the SDS assessment date during Phase C will be used as an event date; If the subject withdraw or discontinue study without meeting the functional relapse criteria, the withdraw/discontinuation date will be the censoring date. For completed subjects, they are considered as censoring at the completion, i.e., time to censor = completion date - randomized date + 1. If time to event/censor is great than 196 days, this subject no matter if he/she discontinued or completed for Phase C will be considered as censoring at Day 196. At interim analysis, the interim analysis cut-off date will be used as the censor date. Log-rank test will be used for the time-to-functional relapse comparisons similar to the primary efficacy analysis.

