5.7 Other Outcome Analysis

5.8 Pooling of small centers

In models such as ANCOVA or MMRM with center included as fixed effect, small centers will be pooled. Small centers will be defined as centers that do not have at least one evaluable subject (evaluable with regard to the primary efficacy variable) in each treatment arm in Phase C. All small centers will be pooled to form “pseudo centers” for the purpose of analysis according to the following algorithm. Small centers will be ordered from the largest to the smallest based on the number of evaluable subjects (i.e.,

subjects who have a baseline value and at least one post-randomization value. The process will start by pooling the largest of the small centers with the smallest of the small centers until a non-small center is formed. This process will be repeated using the centers left out of the previous pass. In case of ties in center size, the center with the smallest center code will be selected. If any centers are left out at the end of this process, they will be pooled with the smallest pseudo centers, or if no pseudo centers exist, they will be pooled with the smallest non-small center.

6 References

E. Glimm, W. Maurer and F. Bretz Hierarchical testing of multiple endpoints in group-sequential trials. *Statist. Med.* **2010**, 29 219—228.

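### The key secondaries are tested at a flat 0.05 at whichever look the primary is rejected, so false-benefit error can modestly exceed 0.025

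*Protocol*

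**What the plan says.** Protocol 7.4.2.1 opens its multiplicity rule with "In order to preserve the overall type I error rate at the 0.05 level, the following testing procedure will be used". If the primary hypothesis "is rejected at an overall nominal alpha level of 0.05", the change in SDS mean total score is tested at 0.05. If that is rejected, time to functional relapse is tested at 0.05. Neither level depends on the look.

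Protocol 7.4.4 gives the primary three looks: 52, 78 and 104 events, at two-sided 0.003051, 0.018325 and 0.044005. A rejection at either interim ends the trial. Section 3.8.1 agrees for the first interim: "If the result of this interim analysis is positive, the trial will be terminated and investigators will be notified".

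Three places in the SAP bear on the point:
- Section 5.5.4.2 has an interim censoring rule for functional relapse: "At interim analysis, the interim analysis cut-off date will be used as the censor date".
- Section 5.5.1.1 requires a further analysis, labelled final, after an interim recommendation. Its alpha is re-derived from the total number of events. This is written for the primary endpoint only.
- The visible text of section 5.5.4 gives the secondaries no hierarchy and no level. However, text in 5.5.1.1 is redacted directly after the boundary paragraph, and the only item in the reference list is a paper titled "Hierarchical testing of multiple endpoints in group-sequential trials".

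**The concern.** A fixed order controls error across endpoints when there is one analysis. Here the primary statistic also decides when the secondary is tested. Relapse and SDS are measured on the same subjects, so their statistics are plausibly positively correlated. A look at which the primary happens to run high is then a look at which a null secondary also tends to run high. Testing it there at the full 0.05 lets the false-benefit rate rise above 0.025.

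That direction matters because the objective is superiority (Protocol 7.1) and only a favourable result supports a claim about function. At stake are two key secondary claims that the protocol presents as error-controlled. The primary test is not affected.

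**Working it through.** **Inputs.** From Protocol 7.1 and 7.4.4: 1:1 allocation, looks at 52, 78 and 104 events, the three nominal levels above, "30% of subjects who receive placebo and 16% of subjects treated with brexpiprazole will relapse in 6 months" and "a hazard ratio of 0.49 (brexpiprazole + ADT versus placebo + ADT) is derived". Not in the documents, so assumed: the correlation ρ between primary and secondary statistics (0 to 1 shown), and the same information fractions (0.5, 0.75, 1) for both endpoints.

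**Step 1: reproduce the plan's design.**
- Hazard ratio: ln 0.84 / ln 0.70 = 0.489.
- Fixed-design events: 4(1.960 + 1.645)² / (ln 0.49)² = 51.98 / 0.509 = 102.1, so 103. The two interim looks raise this slightly. The plan says "104 relapse events are needed in this trial to reach 95% power", and 104 events with the stated boundaries gives 95.0%.
- O'Brien-Fleming-type spending at 0.5, 0.75 and 1 gives 0.003051, 0.018323 and 0.044001, with overall alpha 0.0500. The stated levels are right.
- Critical values for the primary: 2.963, 2.359 and 2.014.
- Drift at the final look: θ = √(104/4) × |ln HR|. At HR 0.49, θ = 5.099 × 0.713 = 3.64. Stopping probabilities in favour of brexpiprazole are then 0.35, 0.44 and 0.16, so an interim stop has probability of about 0.79.

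**Step 2: false-benefit error of the first key secondary.** Let X be the secondary statistic under its null, and let the primary statistic have mean θ√t and correlation ρ with X. The error is the sum over the three looks of

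P(primary first crosses in favour at look k, and X at look k > 1.960).

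Maximised over θ by simulation (2 to 3 million paths), with numerical integration at ρ = 1:

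| ρ | Worst case (nominal 0.025) | At HR 0.49 |
|---|---|---|
| 0 | 0.025 | 0.024 |
| 0.3 | 0.026 to 0.027 | 0.026 to 0.027 |
| 0.5 | 0.028 | 0.027 |
| 0.7 | 0.030 | 0.027 |
| 0.9 | 0.034 | 0.026 |
| 1.0 | 0.039 to 0.040 | 0.025 |

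The range at ρ = 1 reflects the grid of θ: 0.0394 at steps of 0.05 and 0.0398 at steps of 0.02.

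**Step 3: the ρ = 1 case by look.** Take θ = 1.42, which is HR = exp(−1.42/5.099) = 0.757. The primary then crosses when X exceeds 2.963 − 1.42√0.5 = 1.958, 2.359 − 1.42√0.75 = 1.129 or 2.014 − 1.42 = 0.594. All three lie below 1.960, so the secondary threshold binds at each look. The contributions are 0.0250 + 0.0135 + 0.0014 = 0.0398 (from unrounded terms).

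**Step 4: total over both directions.** Counting false rejections either way, the maximum is about 0.050 (0.0505 at ρ = 1). Harm-direction errors fall as benefit-direction errors rise. At ρ = 0.7 and θ = 2 (HR = exp(−2/5.099) = 0.68), the two-direction total is 0.0305, nearly all of it in the benefit direction.

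**Step 5: candidate levels for the secondaries.** Worst-case false-benefit error from the same calculation:

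| Two-sided level at looks 1, 2, 3 | ρ = 0.7 | ρ = 0.9 | ρ = 1 |
|---|---|---|---|
| 0.031 flat | 0.019 | 0.022 | 0.024 to 0.0255 |
| 0.030 flat | – | – | 0.0247 |
| Pocock-type spending, 0.0310 / 0.0208 / 0.0200 | 0.016 | 0.0175 | 0.019 to 0.021 |
| Same as primary | 0.013 | 0.017 | 0.025 |

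Ranges at ρ = 1 again run from a coarse to a fine grid. On the fine grid, flat 0.031 slightly exceeds 0.025 at θ = 1.14 (HR 0.80): 0.0155 + 0.0089 + 0.0011 = 0.0255.

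**The case against.** The strongest reply is that the protocol promises an overall 0.05 with two-sided tests, and on that measure the rule holds: the two-direction total peaks at about 0.05. This stands. A reader might double the benefit-direction figures to 0.056 to 0.079 and conclude that the overall 0.05 is broken. The doubled figure is not the total error, and the documents do not support that conclusion. What remains is the loss of 0.025 control in the direction of the claim.

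Other limits also stand:
- **Effect size.** The worst cases need a weaker primary effect than planned (HR about 0.68 at ρ = 0.7, about 0.76 at ρ = 1). The 79% chance of an interim stop might suggest that the design case is worst, but a strong primary effect reduces the inflation, to at most 0.027.
- **One test each.** A reader might add the nominal levels (0.003051 + 0.018325 + 0.044005 = 0.065) or take the chance of crossing 1.96 at any look (0.098). Neither applies, because each secondary is tested at most once.
- **Timing.** If the secondaries are read at the later analysis in SAP 5.5.1.1, the link to the crossing look weakens. With an assumed 10% to 24% of extra information, the worst case falls to 0.026 to 0.027 at ρ = 0.5 and 0.027 to 0.029 at ρ = 0.7. The SAP does not say which read is confirmatory.
- **Information.** SDS change is analysed by LOCF ANCOVA, so its information need not follow relapse counts.
- **Redaction.** The hidden text in SAP 5.5.1.1, together with the cited paper, may already supply a secondary boundary. It would be wrong to say that the SAP lacks one.

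**Conclusion.** The point holds in a limited form. As written, Protocol 7.4.2.1 does not hold false-benefit error on the first key secondary at 0.025 when the primary can be rejected at any of three looks. The excess is nil at zero correlation, 0.003 to 0.005 at correlations of 0.5 to 0.7, about 0.009 at 0.9 and about 0.015 in the extreme case of perfect correlation. At the planned effect it is at most about 0.002.

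This rests on positive correlation, equal information fractions, and a secondary read at the look where the primary crosses. That last point is an inference, supported by the interim censoring rule for functional relapse. The fixed order of the two secondaries is sound in itself. This is a gap worth closing in the text, not a gross inflation and not a defect that threatens the trial.

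**What to change.** 1. In Protocol 7.4.2.1 and in the SAP, keep the fixed order but replace the flat 0.05 with a pre-specified group-sequential level for each key secondary at the look where the primary is rejected. Pocock-type spending (0.0310 / 0.0208 / 0.0200) holds with room to spare. A flat 0.031 holds for correlations up to 0.9 and sits on the limit at exactly 1; 0.030 holds there too. Reusing the primary boundary is also valid, but leaves only 0.003051 for a secondary read at the first interim.
2. State whether the interim cut or the later final analysis in SAP 5.5.1.1 is the confirmatory read of the secondaries.
3. Confirm that any rule in the redacted SAP text agrees with the protocol, and align the two.

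**Cost.** Wording, plus some power. A key secondary with 80% power at 0.05 has a mean statistic of 1.960 + 0.842 = 2.802. At 0.031 its power is Φ(2.802 − 2.157) = 74%, and at 0.030 it is Φ(2.802 − 2.170) = 74%. Under Pocock-type spending it is 74% at the first look, but Φ(2.802 − 2.312) = 69% at the second and Φ(2.802 − 2.326) = 68% at the third. The primary analysis and the event target do not change.

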7.4.2.2 Other Secondary Efficacy Endpoints

Secondary efficacy measures include assessment of rates of relapse and time-to-relapse for individual relapse criteria. Response, stabilization, and remission rates will also be assessed for brexpiprazole administration prior to randomization. Response is defined based on MADRS and CGI-S criteria, and remission is defined based on MADRS criteria.

Other secondary efficacy endpoints evaluated for the Double-blind Randomized Withdrawal Phase will include:

- Percentage of subjects who relapse
- Percentage of subjects maintaining remission
- Mean change from randomization in MADRS score (LOCF)
- Mean change from randomization in CGI-S score (LOCF)
- Mean change from randomization in each of the SDS individual item scores (LOCF)

Baseline for the Double-blind Randomized Withdrawal Phase (Phase C) is Week 20, which is the last visit of the Stabilization Phase prior to the first dose of double-blind IMP in the Double-blind Randomized Withdrawal Phase. Analysis of the change from randomization for other secondary efficacy endpoints will be based on subjects in the

Protocol 331-201-00079

Phase C Efficacy Sample. Analysis of the CGI-S score endpoint will be based on subjects in the Phase C Efficacy Sample who have post-Phase C baseline CGI-S observations.

For the other secondary efficacy parameters in the Double-blind Randomized Withdrawal Phase, time-to-relapse variables will be analyzed by the same log-rank test and Cox Proportional Hazard model described in the primary analysis, percentage of subjects will be analyzed by the CMH tests adjusting for country, and mean change from randomization variables will be analyzed by an ANCOVA approach using LOCF data, with terms of treatment, center, and baseline as a covariate. As exploratory analyses, MMRM approach with terms of treatment, center, visit, treatment visit interaction, and baseline visit interaction using observed data will be performed.

Descriptive statistics will be provided for the Acute Treatment Phase and the Stabilization Phase. Details of efficacy analyses will be provided in the SAP.

7.4.4 Interim Analysis

Two interim analyses are planned for assessment of efficacy. These analyses are planned to be performed following a group sequential approach at approximately 50% and 75% of events accrual time points and will include all randomized subjects. The second interim analysis (at 75% of events) will be performed only if the first interim analysis is not positive. Subjects who withdraw early from the trial or who are still in the trial at the end of Week 46 will be considered as providing censored observations. The O'Brian-Fleming boundaries will be used for the interim analysis so that the first interim analysis will be conducted when 52 relapse events are available and the second interim analysis, if needed, will be conducted when 78 relapse events are available (Table 7.4.4-1).²⁸ The 2-sided alpha levels for these two interim analyses are 0.003051 and 0.018325 respectively, and the alpha left for the final analysis will be 0.044005. Additionally, a 95% confidence interval for the hazard ratio (brexpiprazole + ADT vs placebo + ADT) will be provided

Protocol 331-201-00079

using the Cox Proportional Hazard model with term of treatment in the model. If the null hypothesis is rejected at either interim analysis time point, the trial will be terminated for having achieved the primary endpoint of a significantly lower incidence with brexpiprazole + ADT compared with placebo + ADT. A separate Relapse Event Evaluation Committee will review and track each relapse event identified and documented. An Interim Analysis Plan will be developed to document the details of data flow and other logistical considerations relating to the interim analyses.

Table 7.4.4-1 Boundaries for Rejection of Null Hypothesis for Interim and Final Analyses		
Analysis	Number of events	2-sided alpha Level^a
Interim analysis #1 (~50%)	52	0.003051
Interim analysis #2 (~75%)	78	0.018325
Final analysis (100%)	104	0.044005

^aObtained using PASS 14 sample size software.

The interim monitoring of efficacy will be performed by an independent IARC (Section 3.7.7). Should the interim analysis be performed at a different time, different frequency, the spending function approach as originally introduced by Lan and DeMets²⁹ will be applied to adjust the critical values in order to guarantee an overall 0.05 alpha level. The spending functions corresponding to O'Brien-Fleming boundaries will be formally applied to the time-to-event analysis (using the log-rank test).

